However, the effective modulation of brain activity may depend not on the absolute current density, but on the current flow that is normal to the cortical surface. This is because the neurons of the cortex are aligned perpendicular to the cortical surface, and the induced current serves to alter neuronal polarization along the apical dendrite to somatic axis of the cortical pyramidal neurons (Datta, Zhou, Su, Parra, & Bikson, 2013). Wagner et al (2004) point out that as little as 30% of the current induced by TMS may be oriented normal to the cortical surface. This implies that TEN, which can be directed from the 256 channel array to be oriented mostly normal to the cortical surface, may achieve effective dosage that is within a factor of 10 less than the magnitude of the effective TMS induced current.

Importantly, a major advantage of TEN over TMS is the ability to reach deep sources. In the simulations of TMS by Wagner, et al. (2004), the depth penetration of TMS was 2 cm into brain tissue, where it reached only the crown of the gyrus, and there the current was largely tangential to the gyral crown (rather than surface normal). We must assume, therefore, that the targeting in the existing studies of slow rTMS for epilepsy (Fregni, et al., 2006; Sun, et al., 2012) was highly approximate. Although Fregni et al. used focal cortical dysplasias to guide targeting, it is highly unlikely that these were all within 2 cm of the cortex, or that effective targeting of current direction was achieved.

Therefore, considering these several factors, we can reasonably expect that the electrical dosage of the GTEN 100, with the safety and comfort level set at $200 \mu\text{A}$ per electrode for the study protocol pulses (**Figure 10**), when targeted appropriately to the epileptogenic focus with the 256 array and the high resolution head model, will be an effective treatment for seizure suppression.

Clinical Feasibility Trial Design

The goal of this unblinded and uncontrolled (“open-label”) feasibility study is to evaluate the safety, comfort, and preliminary efficacy of GTEN 100 treatment in achieving temporary suppression of epileptic activity, as assessed primarily by spikes and secondarily by seizures. The GTEN 100 applies small, electrical currents (up to $200 \mu\text{A}$ per electrode and up to 2 mA total) in a pattern that targets the cortical site of epileptiform discharges in order to decrease the excitability of the epileptogenic cortical tissue.

For this safety and feasibility study, two clinical sites are being planned in the US (Eugene, Seattle) and one in China (Shanghai). An expert epileptologist will provide medical guidance at each site. The Chair of the Study Monitoring Committee will not be associated with these sites or with EGI: [name], Cincinnati Children's Hospital Medical Center. Racial and gender composition will be as it appears in each sample. Study protocols and safety procedures have been approved by IRBs in Eugene and Seattle, and are under review at Huashan Hospital in Shanghai.

Patient Recruitment

Adult and adolescent patients (12 and older, including males and females) are recruited who continue to have seizures after having achieved adequate dosage on each of two antiepileptic drugs. Patients are selected who have focal spikes (and other discharges of focal onset, including seizures) identified through Electrical Source Imaging (ESI) applied to a routine dense array EEG (dEEG) evaluation. All patients agree to maintain their current antiepileptic drug dose throughout the study, including the two month baseline and the two month follow-up period.

Inclusion Criteria

- (1) Partial onset seizures (simple or complex) with failure of adequate seizure control after prior use of at least 2 anti-seizure drugs at effective doses.
- (2) A clearly identified and localizable focus of epileptiform discharges, as defined by the discharges (typically epileptiform spikes) and as identified by dEEG assessment through one or more routine clinical dEEG evaluations.
- (3) Two or more partial seizures, with or without secondary generalization, in the last month, but less than 10 seizures per day.
- (4) Anti-seizure drug regimen has remained unchanged for the month before study entry, and there is reasonable likelihood of stability for the duration of the study, with the exception of allowing short-term rescue medications, such as lorazepam.
- (5) A history of epilepsy for at least 2 years. 33

Exclusionary Criteria

- (1) If of childbearing potential, the patient must agree to use an effective method of birth control during the study and cease participation if pregnant.
- (2) A history or condition of progressive brain disorders, serious systemic diseases, symptomatic cerebrovascular disease, cardiac disease, or alcohol abuse. Special conditions, for example, non-malignant brain tumors and vascular malformations, can be considered for entry on a case-by-case basis.
- (3) A history or condition of status epilepticus or psychogenic seizures.

- (4) Presence of a cardiac pacemaker, vagus nerve stimulator, or metal implantation in the body (other than the teeth) including neurostimulators, cochlear implants, and implanted medication pumps.
- (5) Previous surgery involving opening the skull.
- (6) Allergy to or condition contraindicating lidocaine.
- (7) Unable to express presence of pain or discomfort.

Escape Criteria

For individual patients, the study will be terminated for any of the following reasons:

- (1) Unacceptable discomfort or pain at stimulation currents of 200 μ A.
- (2) A tonic-clonic seizure occurring during a stimulation session.
- (3) Emergence of a first-in-life tonic-clonic seizure at any time during the study.
- (4) Status epilepticus.
- (5) A two-fold increase of seizure frequency over the baseline seizure frequency. If the frequency of seizures is very low, then an apparent increase during treatment (not reliably quantified as a two-fold increase) will be discussed with the patient, family, physician and Study committee.

The entire study will terminate if 5 subjects meet escape criteria.

Baseline Evaluation

During a one-month pre-treatment baseline evaluation period, the patient (and/or family) will maintain the seizure diary, which will be reviewed by the study coordinator in a phone contact once per week. In addition, two two-hour routine dEEG evaluations will be conducted in the baseline evaluation period, including the opportunity for sleep for patients who may have interictal events in sleep or drowsiness. Each baseline evaluation also includes the California Verbal Learning Test, and the Quality of Life in Epilepsy report.

Probe Treatment and Evaluation

The GTEN Plan is developed to apply current pulses to the epileptic focus, as it is identified from the dEEG source localization of the spike onset. The GTEN Plan will often include more than one treatment option, primarily depending on the orientation of the cortical region identified as the epileptic focus. To evaluate a treatment targeting option, a probe treatment may be conducted, consisting of one 17-min pulsed treatment block (Figure 10) followed by one hour of dEEG evaluation and spike counting. If multiple targeting options are evaluated, the one with the best evidence of spike suppression will be selected for the 5 session treatment intervention.

The probe treatment and evaluation protocol is thus a subset (one block instead of 3 blocks of 17-minute pulses) of the approved treatment protocol.

The same GTEN Planning Module is used to develop each probe treatment targeting plan, with the primary difference being the cortical region that is targeted. This is a judgment made by the scientists (Drs. [name] and [name] at EGI) on the basis of the ability to target the cortical region, which is very difficult in medial temporal regions, and the epileptologist ([name] at Harborview) on the basis of the likely relation of the spike development to seizure onset. Often there are multiple possible targets, and the probe treatments and evaluations may allow us to contrast their efficacies.

Treatment Protocol

A two hour GTEN treatment session then targets the identified focal epileptogenic zone for 5 days during one week. For the first ten patients the post treatment monitoring is continued for 3 hours after the treatment session. For those patients whose spikes were more frequent during sleep during the baseline evaluation sessions, an effort will be made to have them fall asleep as the lidocaine takes effect and before the GTEN treatment begins, so that the treatment matches the excitable state during which spikes occur.

All sessions are conducted by personnel who are trained in the dEEG and GTEN 100 operation, including the ability to recognize epileptiform discharges in the dEEG signals. At least one person on the research staff at each session will be certified in first aid in the case that a seizure occurs. The epileptologist at each trial site will provide medical supervision, including recognition of possible adverse events and decision to terminate treatment.

Follow up Protocol

The one week treatment period is followed by a weekly seizure diary review by phone with the study coordinator for six months, plus a dEEG follow up evaluation session in weeks 2, 4, 8, 16, and 24. Each follow up session includes dEEG evaluation during the entire session, including during the review of seizure diary, cognitive function testing with the California Verbal Learning Test, and the Quality of Life in Epilepsy report, as well as a resting dEEG interval. If the patient has interictal events in sleep or drowsiness, the resting dEEG evaluation will include a quiet period for a nap.

Primary Endpoint and Study Success

The primary endpoint is a temporary suppression of epileptic spikes. With assessments of spike rates at weeks 2, 4, 8, 16, and 24, the study will allow estimation of how temporary a suppression is achieved by the one-week treatment. The routine dEEG sessions typically collect dEEG for over an hour, and spike rates per hour will be the standard metric. To be successful, and to warrant progression to a randomized clinical trial, this clinical feasibility study must demonstrate successful targeting and suppression of the epileptogenic zone, as evidenced by temporary but statistically significant spike suppression in contrast to the pre-treatment baseline. All spike rates (baseline, treatment, and follow-up) will be counted as spikes per hour and classified in relation to waking or sleep stage (N1, N2, N3).

Secondary Endpoints and Study Success

The secondary endpoint is monthly suppression of seizures, assessed by the seizure diary each month for six months following treatment, in comparison to the mean seizure frequency for the one-month pre-treatment evaluation baseline. It is clearly advantageous if there is seizure as well as spike suppression as we plan the design of the pivotal trial.

Additional secondary endpoints will be (1) any improvement of cognitive function testing beyond the practice effect (estimated from norms and the improvement in the sham control group); (2) any improvement in quality of life ratings.

Study Monitoring Committee

The safety and comfort decisions for each patient are made by the epileptologist at each site. The safety, comfort, and efficacy of each treatment protocol across sites are reviewed by the Study Monitoring Committee. Vigilance will be maintained throughout the pivotal study to insure safety (no provoked seizures and no adverse effect to non target brain regions). Treatment will be discontinued for any patient that shows treatment-induced seizures, defined as seizures that are not the patient's typical seizures or that occur twice as frequently as the patient's typical seizures, as assessed during baseline. If there are more than five patients with worsening seizures (meeting escape criteria as stated above), the treatment will be suspended at that site. The Study Monitoring Committee (and the FDA when possible) will decide if the trial with that treatment should be terminated at all sites.

At each site, careful attention will be given to the dosage that patients tolerate well, primarily in relation to maintaining adequate comfort with the treatment current and the lidocaine anesthetic. We are confident from the pre-clinical studies that these protocols are tolerated by normal volunteers, and should be comfortable patients with epilepsy. If the electrical dosage needs to be adjusted for individual patients, then the quantitation of cortical target dosage and the dose-response analysis will provide an indication of dosage efficacy (at varying dosage levels) across the entire trial.

Quantitating the Estimated Effective Dose

Because the effective (surface normal) targeting varies across patients according to the location of the epileptogenic zone, the data analysis will attempt to predict the criterion of seizure suppression from the quantitation of effective dosage for each patient. Eventually, this quantitative prediction may allow indications for use that are gauged in relation to the estimated targeting effectiveness in the pre-treatment GTEN planning process. If successful, the adaptive estimation of effective cortical dosage would allow the physician to (1) localize the epileptogenic zone with dEEG, (2) conduct an initial analysis GTEN Planning Module of the effective dose that can be delivered with the 256 array with the 2 mA dose level, (3) conduct a pilot session to determine if the patient is comfortable with the dose required for efficacy, and then (4) discuss with the patient whether GTEN treatment is a worthwhile option. Post hoc analysis of the effective targeting in the clinical feasibility trial will provide initial evidence of the importance of cortical surface normal targeting dosage in predicting seizure suppression.

Power Analysis and Missing Data Analysis

This clinical feasibility trial will test for a statistically significant suppression of epileptic spikes at several time points (weeks, 2, 4, 8, 16, and 24) following treatment in contrast to the average of two dEEG evaluations during the one-month baseline. Without previous results on the Pulsed GTEN treatment, it is difficult to estimate effect sizes for power analysis for this one-week treatment intervention.

As pointed out by the FDA reviewer, an extensive statistical plan may not be warranted for a feasibility study. Furthermore, although we have considered the results of the rTMS study of Sun et al (Sun et al., 2012) to provide some indication of effect size, we agree that we have little basis for estimating the power required for determining the significance of spike suppression with GTEN therapy. We do plan to follow the reviewer's suggestion to compare spike rates following treatment to those from the baseline assessment with a one-sided t-test with a significance level of 0.025.

At the same time, we recognize that we are proposing to evaluate two protocols (Sustained Blocked tDCS and Pulsed GTEN), and must have sufficient numbers of patients to demonstrate feasibility, and to examine the significance of spike suppression, for either treatment protocol. If one protocol is effective and the other is not, we propose to stop enrolling patients for the ineffective protocol and focus recruitment on the effective one to demonstrate efficacy for a pivotal study.

Study Procedures

Informed Consent

Both the recruitment information and the informed consent document explain several aspects of the study:

- GTEN (Geodesic Transcranial Electrical Neuromodulation) is a method of applying small electrical currents through the head in order to achieve a lasting decrease in the neuronal activity of the epileptogenic (seizure-causing) zone of cortex. The experimental treatment protocols have been designed on the basis of previous scientific studies. For the Pulsed TEN, the studies have suggested suppression of epileptic seizures with Transcranial Magnetic Stimulation (in the Fregni, et al., 2006 and Sun, et al., 2012 trials). GTEN is used instead of TMS because of the ability to control the targeting of cortical sites more precisely, as guided by the dEEG fields of the epileptiform discharges. In addition, GTEN is able to target epileptogenic zones in deep as well as superficial cortical sites.
- There is minimal risk of the treatment. The slow pulsed electrical neuromodulation has been applied in several studies of epilepsy with the TMS procedure, and there is no evidence that it causes seizures. Transcranial electrical stimulation (tDCS) has been applied in several experimental studies of patients with epilepsy, with no evidence that it causes seizures. Nonetheless, there is always a small risk of causing seizures, and medical procedures are in place both to monitor for seizures (with the EEG recording in each session) and to provide first aid if a seizure occurs.

- The primary feeling of the electrical current is a tingling sensation, and there is risk of minor itching and/or scalp pain. A small amount of lidocaine is mixed in the electrolyte to minimize the pain at the electrode site, and the procedures will be adjusted to assure that any discomfort is acceptable to the patient. Each patient should understand that they should speak up if there is any discomfort, that the technician is trained to carefully monitor their comfort level, and that they can quit the treatment at any time by simply saying they want to quit. If there is any emergency, the patient is shown how to simply pull the Geodesic Sensor Net off the head.

Changes to the Harborview Informed Consent Form

The Informed Consent Document (ICD) approved with the GTEN IDE was the EGI Consent Form (GTEN) 12/29/2014. This was rewritten to conform to the format of the University of Washington IRB and approved by the UW IRB. It was then modified to include the probe test (as described in the present protocol) and approved in November 2015. A minor error (stating the probe test was 10 min rather than 17 min) was corrected and the correction was approved March 9, 2016.

The EGI Parental Consent Form approved with the IDE is unchanged, but is not in use because the only active trial site (UW Harborview) is not enrolling adolescents.

Both the EGI IRB Consent form of December 29, 2014 (approved with the IDE) and the UW IRB Consent Form (proposed for this trial with the present Supplement) are attached.

With the exception of the probe test, there are only minor differences in these consent forms, involving the change of format to the UW IRB Consent Form format. Following is a section-by-section summary of the revision, emphasizing where the same information from the (IDE approved) EGI IRB Consent Form is included in the UW IRB Consent Form.

Purpose of the Study: This was rewritten to be easier to read. It contains a similar description of treating epileptic discharges with small currents applied to the brain.

Study Summary: added to fit the UW format. This section gives an overview of the study. It describes the evaluation and treatment phases, including the probe test, as well as the follow ups sessions. This information is contained in **Study Procedures** in the EGI form.

Study Procedures: This describes the specifics of each baseline, treatment, and evaluation session, including the CVT and QOLIE.

Risk, Stress, or Discomfort: This was rewritten in the required UW format: it describes the same concerns covered in the EGI form: discomfort, skin irritation, adds risk of loss of privacy and psychological risk of ineffective treatment. This mentions the (very minimal) risk of silver allergy (from the AgCl electrodes) that was discussed in an EGI GTEN Hazard Review (since the IDE). It emphasizes risk of seizures and the procedures for seizure monitoring, in a very similar way as the EGI form.

Benefits of the Study: The important statement is that there may be no benefits, similar to the EGI form.

Source of Funding: This was added following the UW format, and explains EGI's financial support for the trial (equipment, 25% salary for [name], and full salary for [name]).

Confidentiality of Research Information: Emphasizes procedures to maintain, and possible limits, similar to the EGI form.

Alternative to Taking Part in This Study and Other Information cover the information that is described in the **Participation** section of the EGI form.

Localizing Epileptiform Discharges (EDs)

The cortical target for GTEN treatment will be determined from ESI applied to epileptiform discharges (spikes) observed during one or more routine (typically half hour or 40 minute) dEEG evaluations. A nap or sleep EEG may also be collected if seizures typically occur during sleep or sleep transition. EDs will typically involve spikes or sharp waves, although more complex seizure-like EDs and clinical seizures recorded during the routine dEEG will be included. A variant of the protocol is identification of the GTEN targeting through localization of seizure onset, such as with long term video dEEG monitoring.

The GTEN Planning Process

Given the selection of the epileptogenic treatment target from the pre-treatment 256 dEEG evaluation exam with electrical source imaging (ESI), and prior to the first treatment session, the source-sink electrode pattern for targeting is derived through reciprocity with the interictal epileptic focus site with the Geodesic Reciprocity Inverse Process (GRIP). First, the cortical site of spike onset is used to generate the forward projection, from an equivalent dipole at that cortex site to the 256 electrodes (**Figure 4**). By reciprocity, the inverse of this forward projection then defines the optimal sink pattern (from the negative potentials) and the source pattern (from the positive potentials) to be used for the current injection electrodes to achieve current flow normal to the cortical surface (in other words, in the same orientation as the ESI source dipole vector) at the target region.

Next, minimization of non-target current delivery is evaluated for variations of the GRIP pattern, with the Discriminative Cortical Surface Vector (DCSV) method. Typically five to ten different DCSV patterns are used, each with effective delivery to the target and maximal variation of current delivered to non-target areas compared to the other patterns. As described above, given the laminar arrangement of cortical neurons, the efficacy of electrical current in modulating membrane and synaptic activity appears to depend on the delivery of electrical current normal (perpendicular) to the cortical surface (along the dendritic-soma axis) at the site of the epileptogenic zone (as estimated by the site of spike onset). The effective dose computed by the dot product of the current delivery with the cortical surface vector, summed over the

treatment session, will serve as a measure of targeting efficacy and will be retained as a covariate for statistical analysis of treatment efficacy.

bEIT Validation of the Head Model

Once the GTEN Targeting is complete, the first treatment session is scheduled. At the beginning of that first session, the bounded Electrical Impedance Tomography (bEIT) procedure (**Figure 6**) is used with the selected sink-source electrode targeting configuration to test the prediction of the electric head model developed for that subject (with the individual's MRI or the atlas MRI and finite difference modeling). If the mean prediction of the recovered bEIT signal across recording electrodes is not within 10%, the model is judged to be flawed and the treatment is postponed until an accurate targeting model is created.

Once an accurate targeting model is achieved for the sink and source electrodes of the patient's GTEN Targeting of the presumed epileptogenic zone, it can be used for the subsequent treatment sessions, with the restriction that the placement of the Geodesic Sensor Net is replicated (within 2mm desired accuracy) in each session. Accurate placement is verified in each session with the Geodesic Photogrammetry System (**Figure 2**).

Iontophoretic Electrode-Skin Impedance Conditioning and Lidocaine Topical Anesthetic

Because scalp abrasion is prohibited, the electrode-to-skin impedance of the Geodesic Sensor Net typically begins at 50K to 100K Ohms. For consistent and effective delivery of electrical currents for neuromodulation, impedances of 20K Ohms are preferred. Furthermore, given the single current source of the GTEN 100, it is preferable to have all source (anodal) and sink (cathodal) electrodes at about the same impedance level (so that they divide the current evenly at about the 200 μ A per electrode target).

Electrode-scalp impedances will be conditioned with the Dermal Iontophoretic Bond (DIB) protocol, a (patent pending) method of using iontophoresis to carry ions from the electrolyte across the stratum corneum (dead layer) of the skin with DC current, thereby decreasing impedance to the desired level. By including lidocaine in the electrolyte solution, we will anesthetize the scalp and skin under the electrode to minimize superficial nerve pain from the electrical stimulation. Similar to the iontophoresis that is widely used for drug delivery (for example for delivering pain relievers in sports medicine), the iontophoretic impedance conditioning is safe, can be adjusted to be painless for each subject, and can be carried out in parallel with impedance testing at the beginning of the dEEG or GTEN session. The lidocaine is delivered during the conditioning procedure through anode electrodes, with cathodes adjusted to minimize any current flow through the brain. Over several minutes of the 200 μ A/electrode current level of GTEN 100 treatment, we typically observe the (non-abraded) electrode-scalp impedance to drop to 20K Ohms, and occasionally to 10K Ohms. These impedance levels will then be monitored at multiple points during the treatment session.

Setting Current Levels and Administering Treatment

The goal is to optimize the current delivered at the target epileptogenic site, while limiting overall current delivery to 2 mA, and limiting the current applied to each electrode to about 200

μ A. Once the targeting is planned for each subject, the first session will evaluate the comfort level, and current levels adjusted to insure they are acceptable to the patient.

Treatment is applied in a two-hour session (including post session dEEG monitoring), 5 days per week for 1week. For the first ten patients with each treatment, the first treatment session is followed by 3 hours of dEEG monitoring to insure there are no seizures. After that the post-treatment dEEG monitoring is continued for 30 min.

Review of the EEG for Safety and for Spike Counts

The dEEG is reviewed after each treatment and follow up session, by visual inspection by a trained electroencephalographer and with an automated spike detection and clustering algorithm (EGI's Spike Beacon software), with the quantitation reported as a trial endpoint. If there is an apparent change in the spike (and possibly seizure) localization, as indicated by the spike topography clustering, Electrical Source Imaging is conducted with GeoSource to determine if there is a change in localization. If there is a change in localization, or if there is an increase in spike frequency of over one standard deviation compared to the baseline sessions, or if there is non typical seizure activity, the results are conveyed to the epileptologist supervising the clinical trial to evaluate the risk for the patient's continuation of the trial.

The experimental procedures for each patient session are summarized in Table 2.

Monitoring of Risk

A daily diary with a count and description of seizures is reviewed at each session (treatment and follow up). If there is an increase in seizures of two-fold over the patient's baseline levels, the patient's treatment is suspended and the safety of the treatment is evaluated by the epileptologist, patient, and family. In the follow up sessions, routine dEEG evaluations, cognitive function assessments, and quality of life ratings are conducted once each week for three weeks following the treatment, and then week 8. At each follow up session, cognitive function is assessed with the California Verbal Learning Test, a widely used and easily administered test (www.pearsonclinical.com), and quality of life is assessed with the Quality of Life In Epilepsy Questionnaire (http://www.rand.org/health/surveys_tools/qolie.html).

Overview of Study Protocol

Table 2 presents an overview of the treatment protocol. An exception is that for the first ten patients the dEEG will be monitored for seizures for 3 hours after the first treatment session.

Session	Procedure
Pre-Treatment Evaluation	Review of seizure diary each week for one month. Two routine dEEG evaluations to capture epileptiform discharges (ED), including spikes and seizures. MRI when available to determine possible malformations of cortical development and build individual head model.

Session	Procedure
First Treatment Session	
 • Review of seizure diary. • Application of the Geodesic Sensor Net. • Geodesic Photogrammetry System (GPS) to localize sensors. • bEIT scan to verify electrical head model. Lidocaine iontophoresis conditioning during this scan. • 10 minutes resting dEEG. • GTEN treatment: 3 sets of 500 pulses (600s intervals between sets) or 3 sets of sustained tDCS with the same intervals. • 30 minutes resting dEEG (unless sleep EEG needed, then 2 hrs). • California Verbal Learning Test • Quality of Life Questionnaire
Treatment Sessions 2-5	
 • Review of seizure diary. • Application of the Geodesic Sensor Net. • Geodesic Photogrammetry System to localize sensors. • 10 minutes resting dEEG. Lidocaine iontophoresis conditioning during this time. • GTEN treatment, 3 sets of 500 pulses (600s intervals between sets) or 3 sets of sustained tDCS with the same intervals. • 30 minutes resting dEEG (unless sleep EEG needed, then 2 hrs). • California Verbal Learning Test • Quality of Life Questionnaire
Follow up routine dEEG, weeks 2, 4, 8, 16, and 24.	
 • Review of seizure diary. • Application of the Geodesic Sensor Net. • Geodesic Photogrammetry System to localize sensors. • 30 minutes resting dEEG (unless sleep EEG needed, then 2 hrs). • California Verbal Learning Test • Quality of Life Questionnaire

Table 2. Summary of treatments and assessments.

Bibliography

- Bae, E. H., Schrader, L. M., Machii, K., Alonso-Alonso, M., Riviello, J. J., Jr., PascualLeone, A., & Rotenberg, A. (2007). Safety and tolerability of repetitive transcranial magnetic stimulation in patients with epilepsy: a review of the literature. *Epilepsy & behavior : E&B*, 10(4), 521-528. doi: 10.1016/j.yebeh.2007.03.004

- Bergey, G. K. (2013). Neurostimulation in the treatment of epilepsy. *Exp Neurol*, 244, 87-95. doi: 10.1016/j.expneurol.2013.04.004
- Bertram, E. (2007). The relevance of kindling for human epilepsy. *Epilepsia*, 48 Suppl 2, 65-74.

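### The escape rule ends the study, not only treatment, for patients whose seizures worsen after the one-week treatment; other sections stop treatment only, so the protocol conflicts on whether these patients stay in follow-up

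*Protocol*

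**What the plan says.** Under Escape Criteria the protocol lists five reasons, introduced by "For individual patients, the study will be terminated for any of the following reasons". Criterion 1 is unacceptable discomfort at the stimulation current and criterion 2 is a tonic-clonic seizure during a stimulation session. Criterion 3 is "Emergence of a first-in-life tonic-clonic seizure at any time during the study". Criterion 4 is status epilepticus. Criterion 5 is "A two-fold increase of seizure frequency over the baseline seizure frequency", with a discussion in place of the rule where seizures are very infrequent. The section closes with "The entire study will terminate if 5 subjects meet escape criteria".

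Under Treatment Protocol: "A two hour GTEN treatment session then targets the identified focal epileptogenic zone for 5 days during one week". The Follow up Protocol section then sets out the observation: "The one week treatment period is followed by a weekly seizure diary review by phone with the study coordinator for six months". Spike recordings by dEEG are due at weeks 2, 4, 8, 16 and 24. Under Primary Endpoint and Study Success, progression to a randomized trial requires "temporary but statistically significant spike suppression in contrast to the pre-treatment baseline"; the Power Analysis section plans a one-sided t-test at 0.025. The secondary endpoint is monthly seizure frequency from the diary over six months against the baseline month.

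Two other sections address a doubling of seizures. Study Monitoring Committee says treatment is discontinued for that patient. Monitoring of Risk says treatment is suspended and its safety is then evaluated. Neither says that the patient leaves the study.

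**The concern.** The word that matters is what gets terminated. Stopping stimulation in a patient who worsens is a clinical decision and is not in question here. Ending the study for that patient is a different act: once the treatment week is over, all that remains to end is observation. The patients who lose their remaining visits are then selected by a bad outcome.

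Three things are at stake. The seizure endpoint is measured on the variable that triggers criterion 5, so removing those patients lowers the retained mean directly. The spike test, which decides whether the programme moves on, has no concurrent control to absorb selective loss. And a study whose first stated goal is safety would stop watching patients with new tonic-clonic seizures, status epilepticus or doubled seizures. An analysis plan can set a rule for missing values but cannot recover recordings that the protocol stopped making.

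**Working it through.** The protocol states no sample size, effect size or SD, so there is no design figure to reproduce beyond the 0.025 level. The check has three steps.

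**1. Which criteria can act after treatment ends.**

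| Criterion | Can arise in weeks 2-24? |
|---|---|
| 1 Discomfort at stimulation current | No, needs stimulation |
| 2 Tonic-clonic seizure in a session | No, needs stimulation |
| 3 First-in-life tonic-clonic seizure | Yes, any time in the study |
| 4 Status epilepticus | Yes, no time limit given |
| 5 Two-fold seizure frequency | Yes, no time limit given |

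The point rests on criteria 3 to 5. For criterion 5 the sections give three consequences: study terminated (Escape Criteria), treatment discontinued (Study Monitoring Committee), treatment suspended and evaluated (Monitoring of Risk). Only the first removes follow-up data.

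**2. Seizure endpoint.** Assumptions: Poisson monthly counts, no treatment effect, a baseline month of at least 2 seizures (the entry minimum), escape when a follow-up month reaches twice the baseline month. The protocol does not say over what period the doubling is measured; monthly is one reading. The simulated chance that at least one of six months qualifies is:

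| Mean seizures per month | 2 | 4 | 8 | 15 | 30 |
|---|---|---|---|---|---|
| Chance of escape | 31% | 39% | 27% | 12% | 2% |

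At 8 per month, all patients together show about 0% change at month 6. Those who did not escape in months 1 to 5 show about a 12% reduction that is not real. No link between seizures and spikes is needed for this. At the lowest rates the protocol's discussion clause may replace the rule, so those columns are upper illustrations.

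**3. Spike test.** Assumptions: N = 20, true mean change 0, normal changes, correlation r between seizure change and spike change, and the k patients with the largest seizure worsening missing at the tested visit. Under the Escape Criteria section the whole study stops at 5, so k is at most 4 in a study that completes.

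Expected change in those retained = r × (mean of the lowest 20 − k of 20 standard normal values). That mean is −0.182 for k = 2 and −0.332 for k = 4. At r = 0.5 this gives −0.091 SD and −0.166 SD. With an assumed SD of 0.8 on the log scale, exp(−0.8 × 0.091) = 0.93 and exp(−0.8 × 0.166) = 0.88: apparent reductions of about 7% and 12%.

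Simulated one-sided rejection at nominal 0.025:

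| Patients removed | r = 0 | r = 0.3 | r = 0.5 | r = 0.7 |
|---|---|---|---|---|
| 2 of 20 | 2.5% | 4.3% | 6.0% | 8.8% |
| 4 of 20 | 2.5% | 6.0% | 10.3% | 17.5% |

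If only half of the escapers are missing at the tested visit, the range over r = 0.3 to 0.7 falls to 3.2-4.7% (two escapers, one missing) and 3.8-6.6% (four escapers, two missing).

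**The case against.** The strongest answer is that the sponsor may have meant only that treatment stops. Two sections say just that for a doubling of seizures, Monitoring of Risk has the diary reviewed at follow-up sessions, and no section says outright that escaped patients miss the week 2 to 24 visits or leave the analysis. A reader might infer from the escape wording that the worst outcomes are certain to be removed from the spike test. The text does not support that: it supports a contradiction, with data loss under one of its readings.

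A reader might also infer that the spike result must drift toward suppression. That does not follow either. The criteria are seizures and discomfort, while the test is on spikes per hour. Bias needs a positive correlation between the two changes, for which the protocol gives no value. Some doublings would be counting noise, as step 2 shows, and noise need not track spikes.

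The size is open too. The 5-subject stop limits removals, although the Study Monitoring Committee section words its cap differently (more than five patients, by site). Visits before escape remain, and success requires only temporary suppression, so early visits with few escapes may decide it. Analysis sets and the handling of missing visits may properly sit in an analysis plan.

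These objections stand as limits on size and certainty. They do not remove the conflict between sections, the direct effect on the seizure endpoint, or the loss of safety observation if the escape wording is applied.

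**Conclusion.** The concern holds in conditional form. The protocol is inconsistent on whether a patient who meets an escape criterion stays in follow-up. If the escape wording governs, seizure data are lost on the endpoint's own variable, which favours suppression, and safety observation ends in the patients who worsened.

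For the spike test the effect depends on an unknown correlation. Under the stated assumptions, rejection with no true effect is about 4-9% with two of 20 removed and 6-18% with four at correlation 0.3 to 0.7, it stays at 2.5% at zero correlation, and it is smaller when escapers miss only some visits. These figures illustrate direction and order of size; they are not estimates for this trial. The matter should be corrected, since the change is cheap and the spike test decides progression.

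**What to change.** Reconcile the Escape Criteria, Study Monitoring Committee and Monitoring of Risk sections on what meeting a criterion stops. The clinical criteria and the treatment-stopping rule remain for the sponsor to settle.

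Separately, state that meeting an escape criterion does not end data collection. The seizure diary and the planned dEEG visits continue unless the patient withdraws consent, and these patients stay in the spike and seizure comparisons. Record any change of antiepileptic drug after escape, because patients enter on the understanding that doses stay constant and a change would affect later spike rates.

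The cost is protocol and consent wording; the visits are already scheduled. The downside is a slightly less favourable estimate, and some spike rates after escape may reflect drug changes and not GTEN.
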